### **3 STUDY OBJECTIVES**

The objective of this study is to assess the long-term safety of Olumacostat Glasaretil Gel, 5.0%, in subjects with acne vulgaris.

This study may be stopped once at least 100 subjects have been treated for 36 weeks.

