#### **6.1.7 Examination of Subgroups**

As applicable, data will be summarized in total and by treatment received in ACN03/ACN04.

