## 6.8 Safety Evaluation

### 6.8.1 Extent of Exposure

The extent of exposure to study drug in each treatment group will be summarized by total number of days of exposure, total number of applications, number of missed applications, amount of study drug used, amount of study drug per day, percent compliance and number and percentage of subjects who are compliant. A subject will be considered compliant with the dosing regimen if the subject applied 80-120% of the expected number of applications while enrolled in the study.

For subjects receiving Olumacostat Glasaretil Gel, 5.0% in ACN03/ACN04, the date of first application will be from ACN03/ACN04. For subjects receiving Olumacostat Glasaretil Gel, Vehicle in ACN03/ACN04, the date of first application will be from ACN05.

Total number of days of exposure will be computed as follows:

$$\text{Total Exposure} = \text{Date of Last Application} - \text{Date of First Application} + 1.$$

Dosing deviations reported for areas other than the face will not be considered in calculations. On the date of first application and the date of last application, some subjects were to apply one dose and others were to apply two doses, depending on the time of the study visit. After the date of first application and before the date of last application subjects were expected to apply two doses. Missed applications will be calculated from dosing deviations which report zero or one application on a given date. Extra doses will be calculated from dosing deviations which report more than the expected number of applications on a given date.

For subjects receiving Olumacostat Glasaretil Gel, 5.0% in ACN03/ACN04, the total number of applications will be the sum of the applications from ACN03/ACN04 and ACN05, as dosing deviations are specific to the dates of first and last application within each study. The methodology below will be applied to ACN03/ACN04 and ACN05 data separately, then summed.

The total number of applications will be calculated as follows:

If the Date of First Application is not equal to Date of Last Application, then

$$\begin{aligned} \text{Total Applications} &= 2 * (\text{Date of Last Application} - \text{Date of First Application} - 1) \\ &\quad + \text{Expected Applications on Date of First Application} \\ &\quad + \text{Expected Applications on Date of Last Application} \\ &\quad - \text{Missed Applications} + \text{Extra Applications.} \end{aligned}$$

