## 6.8.2 Adverse Events

AEs from ACN03/ACN04 will be included in the analysis for study ACN05. All AEs will be classified on the basis of Medical Dictionary for Regulatory Activities (MedDRA) terminology. Treatment-emergent AEs (TEAEs) are defined as AEs with an onset on or after the date of the first application of Olumacostat Glasaretil Gel, 5.0% (from ACN03/ACN04 or ACN05). If treatment-emergent status cannot be determined (e.g., unknown date of first application), the AE will be considered treatment-emergent. AEs noted prior to the first study drug administration that worsen after baseline will also be reported as AEs and included in the summaries.

TEAEs will be summarized in total as well as by 12-week periods based on time of onset in relation to date of first application of Olumacostat Glasaretil Gel, 5.0%, based on the definitions below.

- 0-12 Weeks            0 <= onset day <= 85
- >12-24 Weeks        86 <= onset day <= 169
- >24-36 Weeks        170 <= onset day <= 253
- >36 Weeks            onset day >= 254

Summaries will present the number of subjects reporting a TEAE by system organ class (SOC), preferred term, severity, relationship to study drug (causality), and seriousness. When summarizing TEAEs by severity and relationship, each subject will be counted once within a SOC or a preferred term by using the event with the greatest relationship or highest severity within each classification.

All information pertaining to an AE noted during the study will be listed by subject, detailing verbatim term given by the PI or designee, preferred term, SOC), onset date, resolution date, severity, seriousness, action taken, outcome and drug relatedness. The event onset will also be shown relative (in number of days) to date of first application.

Serious AEs (SAEs) will be summarized and listed using the same methodology as noted above. In addition, a listing of subjects who prematurely discontinued from the study due to an AE will be provided.

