### **6.8.3      Clinical Laboratory Evaluation**

Laboratory data will be presented in a by-subject listing. Any clinically significant laboratory abnormalities will be captured as adverse events. Changes from Baseline in safety laboratory values will be summarized at the final follow-up evaluation using descriptive statistics for the safety population in total, as well as by treatment received in ACN03/ACN04. For subjects receiving Olumacostat Glasaretil Gel, 5.0% in ACN03/ACN04, the final follow-up analysis visit will be Week 48/ET. For subjects receiving Olumacostat Glasaretil Gel, Vehicle in ACN03/ACN04, the final follow-up analysis visit will be Week 36/ET.

Additionally, changes from Baseline in safety laboratory values will be summarized using shift tables according to normal ranges.

If repeat laboratory testing was performed to follow-up on original results, summaries will be based on original results for each visit. If repeat laboratory testing was performed due to unavailable original test results (e.g., poor sample quality, insufficient amounts, etc.) summaries will be based on repeat results for each visit.

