#### **6.8.4.4 Local Skin Reactions (LSRs)**

Local Skin Responses (LSRs) include erythema, peeling, dryness, burning/stinging and pruritus. These will be scored as 0 (None), 1 (Mild), 2 (Moderate) or 3 (Severe). LSRs will be summarized by analysis visit using descriptive statistics. Specifically, analysis visits to be summarized include Baseline and Weeks 4, 8, 12, 16, 20, 24, 28, 32, 36, 40, 44, 48. Each subject's worst post-baseline grade for each LSR will also be summarized. Additionally, the number of subjects who experience mild, moderate or severe LSRs post-baseline will be presented. By-subject listings of all LSRs, as well as subjects with any severe LSRs will be included.

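### Overall TEAE and SAE counts and worst LSR grade combine up to 48 weeks on the gel for prior-active subjects with up to 36 for prior-vehicle subjects, with no common cut-off

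*SAP*

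**What the plan says.** SAP 6.8.2 brings parent-trial AEs into the ACN05 analysis and calls an event treatment-emergent from the first dose of 5.0% gel in either trial. SAP 6.8.1 sets that start: "For subjects receiving Olumacostat Glasaretil Gel, 5.0% in ACN03/ACN04, the date of first application will be from ACN03/ACN04". For prior-vehicle subjects it is the first ACN05 application. SAP 6.8.3 gives the matching end points. For prior-active subjects "the final follow-up analysis visit will be Week 48/ET"; for prior-vehicle subjects "the final follow-up analysis visit will be Week 36/ET".

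On reporting, SAP 6.8.2 states that "TEAEs will be summarized in total as well as by 12-week periods based on time of onset". The measure is the number of subjects with an event, each counted once within a class or term in the severity and relationship tables. SAEs follow the same method, and percentages come from the general rule in SAP 6.1. In SAP 6.8.4.4 each subject's "worst post-baseline grade for each LSR will also be summarized", with no upper limit on the visits used. SAP 6.1.7 adds that, where applicable, "data will be summarized in total and by treatment received in ACN03/ACN04".

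Days of exposure are summarised (SAP 6.8.1) but are not used as a denominator for events. No overall table has a Week 36 cut or a person-time rate. Protocol section 3 adds: "This study may be stopped once at least 100 subjects have been treated for 36 weeks".

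**The concern.** The percentage of subjects with at least one event can only rise as observation continues, and a worst grade over 12 visits can only equal or exceed the worst over the first 9. Two groups with the same underlying risk will therefore show different overall figures if one is watched for 12 weeks longer. The total column is then neither a 36-week nor a 48-week risk, and it shifts with the mix of prior treatments and with the date the study ends.

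Long-term safety is the only objective, so these descriptive tables are the main result. A difference due to follow-up length could be read as cumulative toxicity, or a real difference could be hidden by an opposing bias.

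**Working it through.** **Follow-up from the SAP.** Prior-active: 12 + 36 = 48 weeks. Prior-vehicle: 36 weeks. This matches SAP 6.8.3 and the analysis-visit table in SAP 6.1.3. The ratio is 48/36 = 1.33. Scheduled post-baseline LSR assessments in that table: 3 + 9 = 12 against 9.

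The documents give no event risks, accrual times or prior-treatment split. Everything below is an illustration under stated assumptions, with identical hazards in the two groups throughout.

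**1. Constant hazard, full follow-up.** p48 = 1 − (1 − p36)^(48/36).

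| 36-week risk | 48-week risk | Ratio |
|---|---|---|
| 5% | 6.6% | 1.32 |
| 10% | 13.1% | 1.31 |
| 20% | 25.7% | 1.29 |
| 30% | 37.8% | 1.26 |
| 40% | 49.4% | 1.23 |

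At 30%, the pooled figure is 33.9% if half the subjects are prior-active (0.5 × 37.8 + 0.5 × 30.0) and 35.2% if two thirds are.

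**2. Early-loaded hazard.** Let the first-12-week hazard be k times the later hazard h, with p36 = 30%. Then h = −ln(0.7)/(12k + 24) and p48 = 1 − 0.7 × exp(−12h). For k = 3, 5 and 10, p48 is 34.8%, 33.5% and 32.0%: ratios of 1.16, 1.12 and 1.07. The gap shrinks but remains.

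**3. Selection at entry.** Protocol 5.3.1 requires a completed parent-trial Week 12 visit. Suppose a share s of prior-active subjects with an event in their first 12 weeks never enter. With e1 = 1 − exp(−12kh), the prior-active percentage is [e1(1 − s) + (1 − e1)(1 − exp(−36h))] / (1 − e1·s). For k = 5, h = 0.00425 per week and e1 = 0.225. With s = 0.22 this is about 30%, so the gap has closed. For k = 3 it closes at s of about 0.36. Under a constant hazard it closes only if every such subject is lost.

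**4. Worst LSR.** Assume a 3% chance of a given grade at each visit, with independent visits: 1 − 0.97^9 = 24.0% against 1 − 0.97^12 = 30.6%. Visits within a subject are correlated, so this is an upper bound for that per-visit chance.

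**5. Early stop.** Assume even accrual of 700 over A weeks, no dropout, and a stop when 100 subjects reach 36 weeks. The stop week is 36 + A × 100/700, ACN05 follow-up is min(36, stop − entry), and the weekly hazard is −ln(0.6)/36 (a 36-week risk of 40%).
- A = 26: stop at week 39.7, all 700 entered, mean ACN05 follow-up about 26 weeks. Crude 31% (prior-vehicle) against 42% (prior-active).
- A = 52: stop at week 43.4, when only 700 × 43.4/52 ≈ 585 have entered. Among those 585, mean follow-up is about 21 weeks. Crude 25% against 37%.

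Cutting prior-active follow-up at 36 weeks lowers 42% to 38% and 37% to 34%. Under an early stop, the day-253 cut alone does not equalise the groups.

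**6. Candidate remedies.** With constant hazard and p36 = 30%, a cut at day 253 gives 30.0% in both groups. One overall first-event rate gives 51.5 per 100 subject-years in both (−ln(0.7)/36 × 52 × 100). With an early-loaded hazard the single rate fails. At k = 5, mean time to first event or end of follow-up is 28.3 weeks (prior-vehicle) and 36.5 weeks (prior-active). The rates are 0.300/28.3 × 5200 ≈ 55 and 0.335/36.5 × 5200 ≈ 48 per 100 subject-years, a ratio of 0.87. For k = 3 and 10 the ratio is 0.91 and 0.82. Rates within 12-week periods stay equal at k = 5: about 110 in the first period (5 × 0.00425 × 5200) and about 22 in each later one, in both groups.

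**The case against.** The SAP already contains much of a like-for-like view. Its 12-week TEAE periods run from first active dose in both groups and put onset from day 254 in a row of its own. SAEs follow the same method, LSRs are shown by analysis visit, exposure is summarised and onset days are listed. An attentive reader can see that follow-up differs. That stands, and it limits the point to the cumulative and worst-grade rows. Those rows are not repaired: a subject can have events in several periods, so period counts cannot be added to give a 36-week figure, and SAP 6.8.2 states no period denominators. By-visit LSR tables likewise do not yield a worst grade to Week 36.

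The side-by-side layout is partly inferred. In SAP 6.8.2 the phrase about totals is set against time periods, not treatment groups. The split by prior treatment rests on the conditional wording of SAP 6.1.7, whereas SAP 6.7.1, 6.8.3 and 6.8.4.1 state it outright. If only a total is shown, it still mixes the two spans.

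A reader might infer that the prior-active column is bound to look worse. The documents do not support that. Follow-up length pushes it up, but the Week 12 completion requirement can push it down, and step 3 shows the two can cancel.

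A reader might also infer that one overall exposure-adjusted rate is the cure. Step 6 shows that it can make the longer-followed group look safer when the hazards are identical.

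Finally, the study is descriptive and no test is affected. That is correct; what is affected is interpretation.

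**Conclusion.** The point holds for the overall TEAE and SAE tables and the worst LSR grade. They mix up to 48 weeks (12 LSR assessments) with up to 36 weeks (9), and no common cut is planned. Under a constant, equal hazard and full follow-up, length alone adds 23% to 32% in relative terms for 36-week risks of 40% down to 5%. With a 36-week risk of 30% and events concentrated early, the excess is 7% to 16%. The event risks, accrual and prior-treatment split are all assumptions.

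The net direction of the observed difference is not known, because selection at Week 12 works against the length effect. Early stopping would widen the relative gap, but the protocol permits a stop and does not require one, and the 52-week accrual figures cover only the roughly 585 subjects entered by then. This is a weakness in the main safety displays that should be corrected. It does not invalidate the study.

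**What to change.** - **SAP 6.8.2:** for every overall TEAE or SAE table that is pooled or split by prior treatment, add the number and percentage of subjects with onset through day 253 from first 5.0% dose. Show events from day 254 separately for prior-active subjects.
- **SAP 6.8.4.4:** give the worst LSR grade through analysis Week 36 for both groups, with Weeks 40 to 48 shown separately for prior-active subjects.
- **Keep** the full-follow-up percentages alongside.
- **Optional:** add subjects with an event per 100 subject-years, calculated within each 12-week period and not as one overall rate. Period rates also handle unequal follow-up if the study stops early, which the day-253 cut alone does not.
- **Caveat to state in the SAP:** neither measure removes the selection from requiring Week 12 completion. In the k = 5, s = 0.22 case above, the day-253 cut would show about 26% (prior-active) against 30%.

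The cost is SAP wording and extra table columns, using onset and dosing dates already held; the optional rates need one derived time-at-risk variable. No new data and no change to trial conduct are needed. Any confidence intervals should be labelled descriptive, since Protocol section 4 plans no inferential statistics.

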### **6.8.3      Clinical Laboratory Evaluation**

Laboratory data will be presented in a by-subject listing. Any clinically significant laboratory abnormalities will be captured as adverse events. Changes from Baseline in safety laboratory values will be summarized at the final follow-up evaluation using descriptive statistics for the safety population in total, as well as by treatment received in ACN03/ACN04. For subjects receiving Olumacostat Glasaretil Gel, 5.0% in ACN03/ACN04, the final follow-up analysis visit will be Week 48/ET. For subjects receiving Olumacostat Glasaretil Gel, Vehicle in ACN03/ACN04, the final follow-up analysis visit will be Week 36/ET.

Additionally, changes from Baseline in safety laboratory values will be summarized using shift tables according to normal ranges.

If repeat laboratory testing was performed to follow-up on original results, summaries will be based on original results for each visit. If repeat laboratory testing was performed due to unavailable original test results (e.g., poor sample quality, insufficient amounts, etc.) summaries will be based on repeat results for each visit.

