#### **11.6 Other Safety Data**

Laboratory data will be presented in a by-subject listing. Any clinically significant laboratory abnormalities will be captured as adverse events. Changes from Baseline in safety laboratory values will be summarized at the final follow up evaluation during the treatment period using descriptive statistics or frequency tables as appropriate.

Additionally, changes from Baseline in safety laboratory values will be summarized using shift tables according to normal ranges.

Pulse and blood pressure will be presented as absolute values and changes from baseline using descriptive statistics.

Concomitant medications will be coded using the WHO-Drug dictionary. Concomitant medications will be summarized by treatment, drug class, and preferred term.

Physical examination data will be presented in a by-subject listing.

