### **6. STATISTICAL AND ANALYTICAL PLANS**

#### **6.1 General Methodology**

All statistical processing will be performed using SAS® unless otherwise stated. Data will be summarized using descriptive statistics. No inferential testing or imputations for missing data will be performed.

Categorical variables will be tabulated with frequencies and percentages. Continuous variables will be tabulated with mean, median, SD, and range (minimum and maximum).

Reported AEs and prior and concomitant procedures and therapies will be classified on the basis of Medical Dictionary for Regulatory Activities (MedDRA) terminology. Concomitant medications will be classified on the basis of World Health Organization Drug Dictionary (WHO-DDE) terminology.

The following data will be imported from ACN03/ACN04 (Baseline defined in section 6.1.2):

Subjects receiving Olumacostat Glasaretil Gel, 5.0% in ACN03/ACN04:

- Demographic information: age, gender, race and ethnicity
- Prior and Concomitant medications
- Adverse events
- Local skin reactions (Baseline and Weeks 4, 8, 12)
- Vital signs and weight (Baseline and Weeks 4, 8, 12)
- Investigator Global Assessment of acne (Baseline and Week 12)
- Acne Patient Self-Questionnaire (Baseline and Week 12)
- Laboratory evaluations: hematology, serum chemistries and urinalysis (Baseline)
- 12-lead ECG (Baseline)

Subjects receiving Olumacostat Glasaretil Gel, Vehicle in ACN03/ACN04:

- Demographic information: age, gender, race, and ethnicity
- Prior and Concomitant medications
- Adverse events
- Local skin reactions (Baseline)
- Vital signs and weight (Baseline)
- Investigator Global Assessment of acne (Baseline)
- Acne Patient Self-Questionnaire (Baseline)
- Laboratory evaluations: hematology, serum chemistries and urinalysis (Baseline)
- 12-lead ECG (Baseline)

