### **6.1.2 Baseline Definition**

The baseline value for each parameter will be defined as the last observation prior to first dose of Olumacostat Glasaretil Gel, 5.0%. For subjects receiving Olumacostat Glasaretil Gel, 5.0% in ACN03/ACN04, the baseline values from ACN03/ACN04 will be considered the baseline values for calculations in ACN05. For subjects receiving Olumacostat Glasaretil Gel, Vehicle in ACN03/ACN04, baseline values will most commonly be from the Week 12/study exit visit of ACN03/ACN04. If subjects choose to enroll in this study, study procedures will not be repeated; study sites will carry over the information from the ACN03/ACN04 study to the Day 1 visit for this study.

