**6.1.3 Visit Windowing**

For subjects receiving Olumacostat Glasaretil Gel, 5.0% in ACN03/ACN04, data from ACN03/ACN04 will be included in summaries of ACN05. For subjects receiving Olumacostat Glasaretil Gel, Vehicle in ACN03/ACN04, baseline values will be sourced from ACN03/ACN04 and data from follow-up visits of ACN05 will be used in summaries. The table below details the analysis visits to be summarized and the associated visits from ACN03/ACN04 or ACN05 which will be sourced for each type of subject.

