### **6.8.4      Other Observations Related to Safety**

#### **6.8.4.1      ECG Measurements**

ECG data will be summarized at the final follow-up evaluation using descriptive statistics for the safety population in total, as well as by treatment received in ACN03/ACN04. Descriptive statistics will be provided for the following ECG parameters, for observed values and changes

from Baseline: heart rate (HR), RR duration, QRS duration, PR duration, QT duration and QTc duration. Change from Baseline in ECG abnormalities will also be summarized using shift tables at the final evaluation visit.

Shift tables will be based on the following categories:

- PR Interval: < 100 msec, 100 – 220 msec and > 220 msec;
- QRS Interval: < 50 msec, 50 – 110 msec and > 110 msec;
- QTcF Interval: < 450 msec, 450 – 500 msec and > 500 msec.

For subjects receiving Olumacostat Glasaretil Gel, 5.0% in ACN03/ACN04, the final follow-up analysis visit will be Week 48/ET. For subjects receiving Olumacostat Glasaretil Gel, Vehicle in ACN03/ACN04, the final follow-up analysis visit will be Week 36/ET.

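### Protocol 8.5 and Appendix 1 give two different rules for exit urinalysis, so the SAP 6.8.3 urinalysis tables may describe a clinically selected subset; a smaller improvement is to summarise the Week 12 labs and ECG of prior-active subjects

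*SAP*

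**What the plan says.** **Exit urinalysis.** Three places in the protocol bear on it.
- Section 8.5 (Week 36 exit or early termination) asks for blood samples, then for urinalysis only where there is a clinical indication.
- Appendix 1 has one safety-laboratory row covering chemistry, hematology, serum pregnancy and urinalysis. It is marked at Day 1 and at Week 36/ET, with no condition on urinalysis.
- Section 9.4.4 says labs follow Appendix 1, or are taken more often if clinically needed. Within urinalysis it makes only the microscopic examination conditional.

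SAP 6.8.3 then plans, for labs in general, "Changes from Baseline in safety laboratory values will be summarized at the final follow-up evaluation using descriptive statistics" for the Safety Population in total and by parent-study treatment. It also says "changes from Baseline in safety laboratory values will be summarized using shift tables according to normal ranges". It does not treat urinalysis differently and gives no denominator.

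**Time points for labs and ECG.** Protocol 11.6 states "Changes from Baseline in safety laboratory values will be summarized at the final follow up evaluation during the treatment period". The SAP follows this for labs, and in 6.8.4.1 does the same for ECG: "ECG data will be summarized at the final follow-up evaluation using descriptive statistics for the safety population in total". For subjects who received the 5.0% gel in ACN03/ACN04 (prior-active subjects), SAP 6.8.3 says "the final follow-up analysis visit will be Week 48/ET". SAP 6.1.2 says that for them "the baseline values from ACN03/ACN04 will be considered the baseline values for calculations in ACN05". The import list in SAP 6.1 brings in their parent-study labs and ECG at Baseline only, whereas local skin reactions and vital signs come in at Baseline and Weeks 4, 8 and 12.

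**The concern.** A site reading section 8.5 would test urine at exit only in subjects with a reason for testing. A site reading Appendix 1 would test everyone. The SAP tables would then pool results collected under two rules, or under a conditional rule throughout, while being presented as Safety Population summaries. Nothing in the table would tell the reader that those tested were chosen because something was suspected.

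The lesser issue concerns prior-active subjects. Their Week 12 visit in the parent study is also Day 1 of ACN05. Because their baseline is the parent-study baseline, the blood, urine and ECG results from that visit are on-drug values. They are already collected and carried over (Protocol 8.1, 9.1, 9.4.3), but the lab descriptive statistics and the ECG tables do not use them.

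**Working it through.** **1. Exit urinalysis: the passages side by side.**

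| Source | Day 1 | Week 36/ET |
|---|---|---|
| Protocol 8.1 | urine collected, no condition | – |
| Protocol 8.5 | – | only if clinically indicated |
| Protocol 9.4.4 | per Appendix 1 | per Appendix 1; only microscopy conditional |
| Appendix 1 | marked, no condition | marked, no condition |
| SAP 6.8.3 | baseline for change and shift | final visit, Safety Population |

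In 9.4.4, clinical need can add tests to the schedule. In 8.5, its absence removes one. The two cannot both be followed for a subject with no indication at exit.

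**2. What conditional collection would do to the tables.** Let p be the share of subjects tested at exit, a1 the frequency of a shift to abnormal among those tested, and a0 the frequency among those not tested.
- With full collection the table would show p·a1 + (1 − p)·a0.
- With conditional collection and tested subjects as denominator it shows a1. The difference is a1 − [p·a1 + (1 − p)·a0] = (1 − p)(a1 − a0).
- With conditional collection and the Safety Population as denominator it shows p·a1, which is too low by (1 − p)·a0.

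The first difference is zero if everyone is tested (p = 1) or if abnormality is equally frequent in both groups (a1 = a0). Otherwise it grows with the gap between them. The documents give none of p, a1 or a0, so no size follows. The sign depends partly on a denominator that the SAP does not state.

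**3. Lab and ECG time points, in weeks since the first 5.0% dose.**
- Prior-active: parent baseline = 0; parent Week 12 (= ACN05 Day 1) = 12; ACN05 Week 36 = 12 + 36 = 48. The on-drug points visible here are 12 and 48. The lab descriptive statistics and ECG tables use 48 (or ET), so 1 of 2.
- Prior-vehicle: ACN05 Day 1 = 0; ACN05 Week 36 = 36. There is one on-drug point and it is used, so 1 of 1.
- With Week 12 rows added: prior-active 2 of 2; prior-vehicle unchanged.

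For ECG, both the statistics and the shift tables are explicitly at the final visit. For labs, only the descriptive statistics are. The lab shift-table sentence names no visit. The Baseline-only import suggests the final visit, but that is an inference.

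**4. What already covers Week 12.** The Week 12 target day is 12 × 7 + 1 = 85. SAP 6.8.2 includes parent-study AEs, and its first summary period runs to onset day 85. A clinically significant Week 12 lab abnormality recorded as an AE with onset by then is therefore already summarised. SAP 6.1.3 also says data from all visits are listed.

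**The case against.** On urinalysis, the best reply is that the Appendix 1 mark is shorthand. The same row shows serum pregnancy without its childbearing-potential condition, so the row may simply leave conditions to the text. That is possible. But the same row covers Day 1, where section 8.1 collects urine without condition, and section 9.4.4 sends the reader to the appendix without restoring any condition on urinalysis itself. Shorthand may explain the conflict, but it does not give sites one rule.

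On Week 12, most of the objection stands. The final-visit summary is what Protocol 11.6 specifies, the SAP import list is consistent with it, the values are listed, and clinically significant lab findings reach the AE tables. The parent-study reports may also summarise Week 12; they are not available here. What remains is that listings show no group-level change or shift, and that the AE rule is written for labs, with no matching sentence for ECG.

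Three stronger readings are tempting, and the documents do not support them.
- *The SAP contradicts itself, because 6.1.3 says of prior-active subjects that "data from ACN03/ACN04 will be included in summaries of ACN05".* That section maps source visits to analysis visits. It does not require every assessment to be summarised at every visit, and it provides for visits where no analysis of an assessment is planned.
- *The harm can be measured by the range of exposure times pooled in the Week 48/ET row.* That pooling is a separate feature, and a Week 12 row would leave it unchanged.
- *Very early leavers lose both on-drug draws through the Day 22 limit.* SAP 6.1.3 applies its early-termination windows to vital signs and local skin reactions, and takes other early-termination data as Week 36/ET. The reading that extends the limit to labs and ECG is not established.

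**Conclusion.** The main point holds: the protocol gives two incompatible rules for exit urinalysis, and the SAP tables depend on which one sites follow. The consequence is conditional. If 8.5 is followed, the urinalysis change and shift summaries describe a clinically selected subset and not the Safety Population. If Appendix 1 is followed, this problem does not arise. A reader might infer that the tables are biased by a known amount or in a known direction. The documents support neither.

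The Week 12 point is a worthwhile descriptive addition and not an error or a protocol–SAP conflict. Its extent is one of two visible on-drug time points for prior-active subjects, in the lab descriptive statistics and the ECG tables. The count rests on the visits visible in these documents; other parent-study draws cannot be checked. The unnamed visit for the lab shift tables is a small gap in specification.

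Overall severity: minor.

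**What to change.** **Urinalysis.**
- Reconcile Protocol 8.5, 9.4.4 and Appendix 1 to one rule before exit data are collected.
- In the SAP 6.8.3 urinalysis tables, state the number of subjects with an exit result.
- If collection stays conditional, label those tables as a clinically selected subset.

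The cost is one wording change in the protocol and a stated denominator.

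**Week 12 labs and ECG (optional improvement).**
- SAP 6.1: extend the lab and ECG import for prior-active subjects to Baseline and Week 12.
- SAP 6.8.3 and 6.8.4.1: add Week 12 change and shift rows for that group only, and name the visit or visits for the lab shift tables.
- Footnote the rows: they cover only subjects who completed parent Week 12 and enrolled. They are therefore selected by exclusion criterion 1, which names ECG findings, and possibly by criterion 2.
- SAP 8: record the addition.

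The cost is minor programming on data already collected, and rows that must be read with the footnote. No new assessments are needed, and the final-visit analyses do not change.
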